3.1 Inclusion Criteria

1. Patients with primary liver tumours; hepatocellular carcinoma, intrahepatic cholangiocarcinoma and other primary tumours, up to 7 cm in size, that are difficult to resect due to their position (likelihood of insufficient healthy liver after resection) or inaccessible for treatment with standard ablation techniques because they are located on large hepatic vascular structures (portal veins, hepatic veins or their presence in the inferior vena cava or its immediate vicinity, subcapsular location of many smaller tumours), but are otherwise operable.
2. Patients in which imaging has conformed disease progression after prior therapy with TACE, RFA or percutaneous alcohol injection and who are not candidates for potentially curative treatment, but have a satisfactory performance status and a Child-Pugh score of less than 8.
Patients in groups 1 and 2 are patients for whom the standard treatment options (systemic and/or surgical) have been exhausted. ECT will be offered to these patients as the only therapeutic option. If a patient has a large number of tumours, the tumours that are both unresectable and unsuitable for RFA will be treated with ECT, while any other metastases will be resected or treated with RFA.
3. Patients with smaller tumours that are not suitable for RFA or percutaneous alcohol injection due to their location (used as bridging therapy to liver transplantation)
4. Patients with tumours that are larger than 4 cm in hard-to-reach locations (unsuitable for surgical resection) and unsuitable for other treatment methods.
Patients in groups 3 and 4 are potentially curable using standard treatment. The added ECT used on these patients will not affect the standard treatment recommended in the current guidelines.
5. The patient is offered ECT treatment even if the patient refuses standard treatment options.
6. A primary liver tumour confirmed histologically and/or by a multidisciplinary team for liver disease based on radiological and laboratory diagnostics.
7. Age above 18 years.
8. Life expectancy over 3 months.
9. Performance status (PS) ≥ 70 according to Karnofsky PS or < 2 according to WHO recommendations.
10. Depending on the type of active substance, 2-5 weeks have passed since the last treatment, if any.
11. The patient must understand the treatment process and any side effects.
12. The patient must be able to give consent to participate in a clinical trial ('informed consent').
13. Prior to inclusion in the study, the patient should be treated by a multidisciplinary team for gastrointestinal tumours.

3.2 Exclusion Criteria

1. Any previously confirmed form of cancer other than surgically treated non-invasive uterine cancer or basal cell carcinoma treated with surgery or radiotherapy.
2. Proven visceral and/or bone metastases or diffuse metastases.
3. Life-threatening infection and/or heart failure and/or liver failure and/or other life-threatening systemic conditions.
4. Clinically significant ascites.
5. Significantly reduced lung function.
6. Age under 18 years.
7. Major coagulation system disorders (coagulation system disorders that do not respond to standard therapy, such as vitamin K replacement or fresh frozen plasma).
8. Received cumulative dose of bleomycin $\geq 250 \text{ mg/m}^2$.
9. Allergic reactions to previous treatment with bleomycin.
10. Chronic decrease affecting renal function (creatinine $> 150 \text{ }\mu\text{mol/L}$).
11. Epilepsy.
12. Heart rhythm disorders.
13. Implanted pacemaker or defibrillator.
14. Pregnancy.
15. Patients who are unable to understand the purpose of the study or do not agree to participate in the study.

3.3 Examinations and Tests Before Treatment

Two weeks before inclusion in the study, the following will be performed:

- clinical examination, anamnesis
- radiological imaging techniques to discover liver metastases:
 - dynamic contrast-enhanced ultrasound (DCE-US)
 - computed tomography (CT) perfusion
 - magnetic resonance imaging
- Systemic disease evaluation
 - X-ray or CT of the lungs
 - other examinations depending on the clinical picture (bone scintigraphy, PET/CT)

One week before inclusion in the study, the following will be performed:

- laboratory tests:
 - haematological tests with a complete blood count
 - coagulation tests

- biochemical tests: electrolytes, creatinine, transaminases
- immunohistochemical examinations: tumour markers
- ECG

4 TREATMENT PLAN

Where there are liver tumours (up to 3 cm in maximum diameter) with the lower edge located up to 3 cm below the liver capsule, ECT using short-needle electrodes with a hexagonal geometric arrangement will be performed in line with the standard surgical procedures for treating cutaneous and subcutaneous tumours/metastases with ECT.

Where there are larger liver tumours (up to 5 cm) located near the vena cava or along large hepatic or portal veins, ECT using long-needle electrodes with an arbitrary geometric arrangement will be performed. Using numerical modelling, we will prepare a treatment plan to determine the optimal position of the electrodes and the required electric current voltage for the optimal electroporation of the target tissue. The preparation of a treatment plan using numerical modelling will take place in two basic steps (see below) based on radiological images captured up to 2 weeks before the procedure.

1. Decomposing medical images and constructing a model:
 - importing medical radiology images into an appropriate program,
 - determining important areas,
 - pretreating and decomposing images,
 - constructing a 3D model.
2. Planning treatment:
 - The 3D model will be supplemented with electrodes supplying electroporation pulses, as well as with corresponding tissue properties and boundary conditions based on the calculation using the finite element method and the calculation processed by automatic algorithms for determining the criterion function,
 - the possibility of statistical and probability functions to determine the probability of electroporation will be examined, the effect probability being a function of the electric field strength applied.

[figure not shown]

Figure 1: Schematic representation of electrode placement in the middle and the periphery of a metastasis in healthy liver tissue.

5 TREATMENT: ELECTROCHEMOTHERAPY (ECT)

Patients meeting the inclusion criteria with primary liver tumours for which surgery is not possible due to the proximity of the main hepatic veins, for whom the success of other ablation techniques cannot be predicted, will undergo ECT.

5.1 Chemotherapeutic Agents

- The cytostatic used will be bleomycin (BLM) manufactured by Heinrich MackNachf. GmbH & Co. KG, Illertissen, Germany.
- The BLM will be dissolved in saline solution and administered intravenously with a bolus injection at a dose of 15 mg/m².
- 8-28 min after BLM application, electroporation pulses will be delivered to the metastases.

5.2 Electroporation

5.2.1 Electric Pulse Generator

- We will use the Cliniporator VITAE electric pulse generator manufactured by IGEA, Carpi, Italy, designed to treat larger and deep-seated tumours, such as liver metastases.
- It has the CE mark and is authorized for use in a clinical setting.

5.2.2 Electrodes

Two types of electrodes will be used:

- a) Short-needle electrodes with a fixed hexagonal geometric arrangement:

- for metastases with their lower edge located up to 3 cm below the liver capsule;
- ECT will be performed in line with the standard surgical procedures for cutaneous and subcutaneous tumours/metastases;

b) Long-needle electrodes with an arbitrary geometric arrangement:

- for deeper-seated tumours and tumours located ≥ 3 cm below the liver capsule;
- to ensure the safety margin, the required number of electrodes (presumably from 4 to 6) will be inserted into the tumour and its surrounding area using ultrasound guidance in line with the treatment plan prepared based on numerical modelling before the procedure.

[figure not shown]

Figure 2: Short-needle electrodes with a fixed hexagonal geometric arrangement (a), long-needle electrodes with an arbitrary geometric arrangement (b) and Cliniporator VITAE (c).

5.2.3 Electroporation Pulses

- Between each pair of electrodes, 8 rectangular electroporation pulses (length: 100 μ s) will be supplied to the tumours in two sequences, each containing 4 electroporation pulses of reversed polarity and a repeating frequency of 1000 Hz.
- The delivery of individual pulse sequences will be synchronized with the occurrence of successive heartbeats.
- When using long-needle electrodes with an arbitrary geometric arrangement, the voltage of the electroporation pulses for each electrode pair will be determined on the basis of

numerical modelling, and when using short-needle electrodes with a fixed hexagonal geometric arrangement, a voltage of 730 V will be supplied.

- If excessive electric current (> 50 A) makes it impossible to supply a sufficiently high voltage, a larger number of lower-voltage electroporation pulses will be supplied.

5.3 The Synchronization of Electroporation Pulses with ECG and Holter ECG Recording

- To ensure synchronization, the Cliniporator VITAE will be connected to an AccuSync 42 external unit, which produces trigger pulses based on the measured ECG signal to deliver electroporation pulses on the R wave of each heartbeat.
- For interoperative patient monitoring, patients will be connected to AccuSync via three ECG electrodes independently of ECG capture.
- On the selected ECG lead (standard leads I, II, III; the most suitable lead is chosen depending on the intensity of the R wave), AccuSync detects the R wave of individual heartbeats in the early phase of the increasing R wave slope and produces a trigger pulse.
- The trigger pulse is brought to the Cliniporator VITAE, which uses its built-in synchronization algorithm for the further verification of trigger pulse suitability and, meeting a series of conditions, produces electroporation pulses with a 50 ms delay behind the trigger pulse to avoid ventricular sensitivity (T wave range).
- The ECG signal and trigger pulses will be captured and stored for later analysis of the synchronization algorithm function and of any immediate effects of the treatment on heart function.

6 FOLLOW-UP AFTER TREATMENT

Follow-up will be carried out at three levels. First, defining the early and late effects of treating primary liver tumours using ECT; second, evaluating the short- and/or long-term effects of electroporation pulses, BLM or ECT as a whole on the heart function; and third, recording any adverse effects of ECT.

6.1 Effects of Treating Primary Liver Tumours Using ECT

- Early treatment effects will be assessed using DCE-US or CT based on changes in tumour blood flow after ECT compared to the pre-ECT blood flow.

- Late effects will be assessed based on modified RECIST criteria, taking into account the change in the size and density of the treated tumour nodules before and after ECT. These will be assessed based on CT perfusion imaging; the volume of the metastases will be calculated using the formula $V = \frac{a \times b^2 \times \pi}{6}$, where a is the shorter and b the longer metastasis diameter.

Based on the assessment of the late ECT effects, the response to treatment will be evaluated in line with the WHO classification:

- Complete response (CR): complete disappearance of the tumour nodule
 - Partial response (PR): reduction of the tumour nodule size by more than 50%
 - No change (NC): decrease in tumour nodule size by less than 50% or an increase in the tumour nodule size by less than 25%
 - Progressive disease (PD): growth of the tumour nodule by more than 25%
- The direct effect will be assessed by histological analysis of those metastases that are surgically removed.
 - EORTC Quality of Life questionnaire according to the QLQ C30 standards

EXAMINATION/TEST	Screening period until D -14	D -1	D7	D30	D60	D90	D120
clinical examination, anamnesis	X	X	X	X	X	X	X
ECG	X	X					
DCE-US	X			X	X		X
CT perfusion / MRI	X			X			X
Blood count	X	X	X				
Coagulation tests	X	X	X				
Biochemical blood analysis	X	X	X	X	X		X
EORTC QLQ C30 questionnaire	X		X	X			

*D = day

6.2 The Effects of Electroporation Pulses, BLM or ECT as a Whole on Cardiac Function

- To study the short-term effect, we will use the ECG signal captured during surgery, which will cover the period before, during and immediately after ECT, including BLM injection and electroporation pulses.
- To study possible late and/or long-term effects, the ECG signal will be recorded using a standard Holter system in 24-hour periods immediately before and after surgery. 5-10 patients will be included.

ECG recordings will also be performed on 10-15 patients who will undergo abdominal surgery without ECT at the Department of Abdominal Surgery, University Medical Centre Ljubljana.

6.3 Recording ECT Adverse Effects will be Performed According to the Criteria of the National Cancer Institute (NCI)

An adverse effect is an undesirable and unexpected sign, symptom or disease, regardless of the cause, that develops or worsens during the study and that includes pathological clinical observations and deviations in the values of laboratory-measured parameters. The latter are only considered a side effect if they require additional treatment or result in the premature withdrawal of the patient from the study.

We will record any side effects that occur during the study and up to 30 days after the end of treatment. If a serious adverse reaction occurs more than 30 days after the end of treatment, the principal investigator will decide whether the complication is study-related or not.

We will record the start and end time of any adverse effect and the cause-and-effect relationship between the adverse effect and the ECT, cancer or other diseases, as well as assessing the severity of the adverse effect and describing the actions that will need to be taken.

The causal relationship between the adverse effect and the ECT will be assessed using the following criteria:

- Not related to the study.
- Probably not related to the study.
- Possibly related to the study.
- Probably related to the study.
- Certainly related to the study.

The severity of the side effects will be assessed using the following grades:

- Grade 1 – mild
- Grade 2 – moderate
- Grade 3 – a difficult complication requiring medical care
- Grade 4 – a life-threatening condition requiring immediate medical assistance
- Grade 5 – death

If a serious adverse effect is recorded during the study, the principal investigator will notify the responsible person at the National Medical Ethics Committee of the Republic of Slovenia in writing within 24 hours. A serious adverse effect is a complication that results in the following:

- death,
- a life-threatening condition requiring immediate medical assistance,
- hospitalization or extended hospitalization,
- the prolonged inability of the patient to perform any task that they were able to perform before the onset of the complication,
- any event or condition that endangers the life or health of the patient and that, according to a medical assessment, could lead to any of the serious complications referred to above.

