2 STARTING POINTS

The Principles of Electroporation and Electrochemotherapy (ECT)

By exposing a cell to an external electric field, a transmembrane voltage is established on the cell membrane. When the threshold value is exceeded, this voltage causes electroporation of the cell membrane, i.e. the formation of hydrophilic pores, which allow the increased passage of molecules into the cell.¹

The principle of electrochemotherapy (ECT) is based on exposing the tumour to pulses of electroporation delivered by specific electrodes. This allows the passage of previously applied hydrophilic cytostatics, e.g. bleomycin and cisplatin, into the cells.² Because the intake of cytostatics is only increased in the areas exposed to the electroporation pulses, ECT is a local treatment method. In addition to the direct action of cytostatics on tumour cells, ECT has an indirect vascular-disrupting effect, because cytostatics act on the endothelial cells in the tumour vasculature.³ The doses of cytostatics used in ECT are extremely low, resulting in minimal or no systemic toxicity.⁴ Furthermore, the application of electroporation pulses reduces the blood flow in the tumour, which keeps the cytostatics in the tumour for a longer period, thus making the treatment more effective.³

Clinical Applications of ECT

In the early 1990s, the team at the Institute of Oncology Ljubljana headed by [name], PhD, played an active part in pioneering clinical studies on treating cutaneous and subcutaneous tumours with ECT.⁵ According to the findings of these first clinical trials, an 80% objective response of the treated tumour nodules is achieved using ECT.⁶ Our team also helped draw up and publish standard surgical procedures for treating cutaneous and subcutaneous tumours using ECT. Today, ECT is a well-established method for treating malignant melanoma metastases, especially as part of palliative care,

in 15 European countries. In 2012, 2500 patients were treated with ECT and, according to several databases, ECT is now used in 135 oncology centres.

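### The blood count stops at D7 although adverse effects are recorded to 30 days and blood is already drawn at D30; separately, the lung-function exclusion has no stated function measure

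*Combined protocol and SAP*

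**What the plan says.** Section 6.3 sets the recording period: "We will record any side effects that occur during the study and up to 30 days after the end of treatment". Its definition of an adverse effect includes deviations in laboratory values, but counts them only when they call for treatment or cause the patient to leave the study early.

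The schedule in Section 6.1 has these columns: "Screening period until D -14 D -1 D7 D30 D60 D90 D120". Four of its rows matter here:

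- "Blood count X X X": screening, D -1 and D7.
- "Coagulation tests X X X": the same three visits.
- "Biochemical blood analysis X X X X X X": screening, D -1, D7, D30, D60 and D120.
- "clinical examination, anamnesis X X X X X X X": all seven visits.

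The QLQ-C30 is given at screening, D7 and D30.

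Section 3.2, criterion 5, excludes "Significantly reduced lung function" and gives no threshold. The only lung test in Section 3.3 is an X-ray or CT, listed under systemic disease evaluation before inclusion. The schedule has no lung-function row.

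Section 1 names safety and efficacy as the purpose. Section 7 analyses adverse effects descriptively. Section 2 says, as background: "The doses of cytostatics used in ECT are extremely low, resulting in minimal or no systemic toxicity".

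**The concern.** The cytostatic is given intravenously (Section 5.1), so exposure is systemic, and safety is one of the two stated aims. The recording period runs to at least 30 days, yet the last scheduled blood count is at D7. A fall in counts that produces no symptoms could occur after D7 without any planned test to show it. The documents give no reason why the D30 sample is used for biochemistry and not for a count.

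At stake is how a descriptive safety report can be read. A statement that no haematological effect was seen up to day 30 would rest, after D7, on symptoms and unscheduled tests. Part of the apparent absence could then be absence of measurement.

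The lung question is similar in kind but separate. A patient is excluded for reduced lung function, but nothing says how that is established, and no lung-function measure is repeated after treatment.

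**Working it through.** The plan states no toxicity rate, power or sample-size derivation, so there is no figure to reproduce. The check sets the schedule against the recording window.

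**Inputs.** Window: 30 days after treatment (Section 6.3). Visits and marks: schedule in Section 6.1. Sample size: 10 + 15 = 25 (Section 1). Assumption: D0 is the treatment day, so the post-treatment visits inside the 30-day window are D7 and D30.

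**Step 1. Is the row read correctly?** Other rows keep their internal gaps. Biochemistry, for example, has a blank at D90 before the mark at D120. The blood-count row has three consecutive marks and no gap, so they fall under the first three columns.

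**Step 2. Coverage by visit.**

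| Assessment | D7 | D30 | Visits in the 30-day window | All post-treatment visits |
|---|---|---|---|---|
| Clinical examination | yes | yes | 2 of 2 | 5 of 5 |
| Biochemistry | yes | yes | 2 of 2 | 4 of 5 |
| QLQ-C30 | yes | yes | 2 of 2 | 2 of 5 |
| Blood count | yes | no | 1 of 2 | 1 of 5 |
| Coagulation | yes | no | 1 of 2 | 1 of 5 |
| Lung function | no | no | 0 of 2 | 0 of 5 |

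The last column is relevant only if recording during the study is read as running to D120.

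**Step 3. What can be said when no event is seen?** With n patients assessed and no events, the exact one-sided 95% upper limit for the event rate is 1 − 0.05^(1/n).

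- n = 10: 1 − 0.05^(1/10) = 25.9%.
- n = 25: 1 − 0.05^(1/25) = 11.3%.

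These limits apply only to patients actually assessed. For the blood count they can be given at D7 if everyone attends. At D30 no patient has a scheduled count, so no such limit can be calculated from planned data. With 25 patients, each event found or missed moves the observed rate by 1/25 = 4 percentage points.

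**Step 4. Would a D30 count enter the adverse-effect data?** Only in part. Under Section 6.3 a deviation that is neither treated nor a cause of withdrawal is not a side effect, even when measured. A count alone would therefore add only deviations that lead to action. Milder changes appear only if the laboratory values themselves are summarised, which Section 7 does not mention.

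**Step 5. Lung function.** Other organ-related exclusions have a matching test in Section 3.3. Renal function has a creatinine limit and a creatinine test, coagulation disorders have coagulation tests, and rhythm disorders have an ECG. Criterion 5 has neither a threshold nor a function test. Imaging of the lungs is planned at baseline, but imaging does not measure function.

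**The case against.** The strongest reply is that the window is assessed. Clinical examination with history, biochemistry and the QLQ-C30 fall at both D7 and D30, and adverse effects are recorded throughout. That stands. A reader might infer from the blood-count row that the tests as a whole leave the 30-day window open, but the schedule does not support this: symptomatic, renal and hepatic toxicity can be picked up at D30.

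A reader might also infer that the plan cannot test a premise of minimal or no systemic toxicity. That sentence is background on the method in general. It is not a hypothesis or endpoint, Section 7 is descriptive, and neither test named in Section 8 concerns toxicity.

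Nor does it follow that the reported toxicity rate will be too low. By the protocol's own definition an untreated fall in counts is not a side effect. Only an unnoticed fall that would have needed treatment could be missed, and the documents give no frequency for that.

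Expressing the gap as a share of the days between D7 and D30 would mislead, because a blood count is a measurement at one time and does not cover days.

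On the lung criterion, history, examination and baseline imaging can inform a clinical judgement. It would be too much to say that the criterion cannot be applied; what is missing is a stated measure.

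The documents do not say that counts fall after D7 or that a single dose affects the lungs. The point therefore rests on the mismatch between schedule and window, not on an expected toxicity.

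**Conclusion.** The point holds in a narrow form. An asymptomatic haematological change after D7 has no scheduled test, although the protocol records adverse effects to at least day 30 and draws blood that day. The gap is one of the two visits in the window, for blood count and equally for coagulation; the other planned assessments cover both visits. The effect on the reported toxicity rate cannot be quantified from the documents. What is lost is the basis for a haematological safety statement beyond D7.

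This assumes that D0 is the treatment day and that the table columns are as read above. It is a cheap improvement to a stated aim and does not invalidate the safety assessment.

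The lung-function part is a matter of missing detail: criterion 5, the pre-treatment tests and the schedule do not connect. The documents do not support prescribing a particular respiratory test.

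**What to change.** 1. Reconcile the blood-count row in Section 6.1 with the 30-day window in Section 6.3 by requesting the count on the D30 sample already drawn for biochemistry. State whether ending coagulation tests at D7 is intended.
2. In Section 7, add a summary of laboratory values by visit, with the number of patients assessed at each, alongside the side effects as defined in Section 6.3.
3. If the schedule stays unchanged, limit the haematological safety conclusion to D7.
4. Reconcile criterion 5 in Section 3.2 with Section 3.3 and the schedule, using a measure of the sponsor's own choice, and limit pulmonary safety claims to what was assessed.

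Items 1 and 2 cost one extra laboratory request per patient on an existing draw, at most 25 in all, plus one descriptive table. No new visit is needed. A few more abnormal values may be reported. Item 3 costs only wording. The cost of item 4 depends on the measure that the sponsor chooses.
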